Assessment of Efficacy and Power	The primary estimand will be the adjusted unconditional population difference in the mRS response (i.e., mRS score of 0-2) proportions between treatment conditions (nerinetide vs. placebo) in the target patient population at Day 90. Deaths occurring over the Day 90 period will be considered as non-responses.
	Assuming a 50% overall responder rate for the placebo group population (as observed in the ESCAPE-NA1 trial), there will be approximately 91.3%power to detect an 11.4% absolute effect difference between response rate (proportion of responders, with Day 90 mRS in the range 0 to 2 with nerinetide and placebo, at alpha level 0.25 one-sided (0.05 2- sided), using the planned sample size of 850 evaluable subjects, randomized 1:1, per group [EaST v6.5, 2022].

	The interim analysis is planned to take place at 60% information (primary endpoint), i.e., when approximately 510 of the target 850 patients have reached their primary endpoint assessment. The cumulative alpha spent at the interim analysis is 0.004 and final analysis 0.025, one-sided (0.05 2-sided); the stopping boundaries on the Z scale are 2.668 (interim) and 1.981 (final) and on the p-value scale 0.004 (interim) and 0.021 (final), all on the assumption that the interim is conducted at 60% information.
Statistical Assumptions	The primary and secondary efficacy endpoint analyses will be conducted on the intent-to-treat (ITT) population, defined as all randomized participants, regardless of treatment actually received. The primary analysis will be repeated on the Per Protocol (PP) population. An ITT analysis will also be conducted for the secondary endpoints, with participant grouped according to the randomized (intended) treatment.
	The pivotal primary analysis for the primary estimand model will be a logistic regression model with fixed effects including the treatment group, the stratification covariate of time from stroke onset to randomization \leq 4.5 hours (yes/no) and the randomized minimization factors (age, sex, baseline NIHSS score, occlusion location, time from qualifying imaging to randomization, baseline ASPECT score, sex, and pooled site), and an interaction term of treatment by time from stroke onset to randomization. If the interaction term is not significant at the level of 0.05 it will be removed from the model.

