This sample size was calculated taking into account a dropout/non-evaluable rate of 2% with a lag to primary endpoint assessment of 4 months, estimated accrual rate of 50 participants per month, target effects 0.5 vs 0.6114 and a single interim analysis for early superiority stopping with an O'Brien-Fleming alpha spending function boundary at 60% information (510 evaluable participants). The interim analysis is planned to take place at 60% information (primary endpoint), i.e. when approximately 510 of the target 850 patients have reached their primary endpoint assessment. The cumulative alpha spent at the interim analysis is 0.004 and final analysis 0.025, one-sided (0.05 2-sided); the stopping boundaries on the Z scale are 2.668 (interim) and 1.981 (final) and on the p-value scale 0.004 (interim) and 0.021 (final), all on the assumption that the interim is conducted at 60% information.

See Section 9.4 for further details on the interim analysis.

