9.4 Interim Analysis

There will be an interim efficacy analysis in this trial. It will be conducted by the unblinded statistician in the Independent Statistical Group.

The interim efficacy analysis will be performed after approximately 510 participants have complete the Day 90 follow-up, at 60% information on the primary endpoint. The planned sample size is 850 participants randomized 1:1, allowing for a single interim analysis at 60% information (when about 510 patients have primary endpoint assessments) with O'Brien-Fleming alphaspending function stopping boundary for overwhelming efficacy. The cumulative alpha spent at the interim analysis is 0.004 and final analysis 0.025, 1-sided; the stopping boundaries on the Z scale are 2.668 (interim) and 1.981 (final) and on the p-value scale 0.004 (interim) and 0.021 (final), all on the assumption that the interim is conducted at 60% information .

These calculations were performed by taking into account a dropout/non-evaluable rate of 2% with 4 month lag to primary endpoint assessment, estimated accrual rate of 50 participants per month, target effects 0.5 vs 0.6114 and a single interim analysis for early superiority stopping with an O'Brien-Fleming alpha spending function boundary at 60% information (510 evaluable participants). [EaST v6.5, 2022].

The IDMC may recommend stopping for overwhelming efficacy at the interim analysis if the test statistic crosses the O-F boundary. The IDMC Charter will provide further details on the rationale for, and how, these recommendations will be communicated.

10 SUPPORTING DOCUMENTATION and OPERATIONAL CONSIDERATIONS

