1.4 Sample Size Determination

The primary efficacy outcome variable for the pivotal assessment of efficacy is the overall proportion of participants experiencing a favorable functional outcome 90 days post-randomization, defined as a score of 0 to 2 on the modified Rankin Scale (mRS). These participants are defined to be responders.

An initial target 680, and up to 1020, male and female participants aged 18 or older harboring AIS and who are selected for endovascular revascularization without intravenous or intra-arterial thrombolytic therapy will be enrolled.

Based on results of ESCAPE-NA1 and assuming a 50% overall responder rate for the placebo group, there will be approximately 82% power to detect an 11.4% absolute effect difference between response rate (proportion of responders, with Day 90 mRS in the range 0 to 2) with nerinetide and placebo, at alpha level 0.05 2-sided.

This sample size was calculated via simulation under the assumption of 2% probability of dropout and 50 patients per month accrual during the trial (across both arms) using the Chen-DeMets-Lan approach⁷ for unblinded sample size re-estimation, and possible early stopping for overwhelming superiority with an O'Brien-Fleming alpha spending boundary at a single interim analysis with a maximum sample size of 1020 evaluable (inflation factor 1.5) and inflation in the "promising zone" based on conditional power between 50% and 81%, based on the observed trend at the interim and using a Wald statistic with target conditional power after sample size increase 81% (using an increase rule to be specified in the IDMC Charter to prevent backcalculation of interim effect sizes after the interim analysis). The interim analysis is planned to take place at 75% information (primary endpoint), i.e. when approximately 510 of the initial target 680 patients have reached their primary endpoint assessment. With these specifications, the study will have approximately 82% power for the primary analysis using standard Wald statistic for comparison of 2 independent proportions (EaST v6.5 2020). The cumulative alpha spent at the interim analysis is 0.01 and final analysis 0.025, 1-sided; the stopping boundaries on the Z scale are 2.34 (interim) and 2.012 (final) and on the p-value scale 0.01 (interim) and 0.022 (final), all on the assumption that the interim is conducted at 75% information (EaST v6.5, 2020).

See Section 8 for further details on the interim analysis.

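### The protocol pairs the final Z boundary of 1.981 with p = 0.021, but Z = 1.981 is a one-sided p of 0.0238, so the primary endpoint has two conflicting success thresholds

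*Combined protocol and SAP*

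**What the plan says.** Protocol section 9.1 specifies "a single interim analysis for early superiority stopping with an O'Brien-Fleming alpha spending function boundary at 60% information". It gives the alpha spending as "The cumulative alpha spent at the interim analysis is 0.004 and final analysis 0.025, one-sided (0.05 2-sided") and the boundaries as "the stopping boundaries on the Z scale are 2.668 (interim) and 1.981 (final"). The same sentence then restates them "on the p-value scale 0.004 (interim) and 0.021 (final), all on the assumption that the interim is conducted at 60% information". The Synopsis (Assessment of Efficacy and Power) has the same pairing, "the stopping boundaries on the Z scale are 2.668 (interim) and 1.981 (final) and on the p-value scale 0.004 (interim) and 0.021 (final"), and section 9.4 repeats it, "on the p-value scale 0.004 (interim) and 0.021 (final").

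Table 9-1 of the protocol says that the primary p-value comes from the cited covariate-adjusted method for a difference in proportions and that the overall one-sided level of 0.025 is adjusted for the interim. Section 9.3.2 places the primary test first in a fixed sequence, ahead of the secondary endpoints.

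The SAP (v2.0, sections 1.4 and 8.1) describes a different design, with the interim at 75% information. There, final Z = 2.012 is paired with p-values given "on the p-value scale 0.01 (interim) and 0.022 (final").

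**The concern.** A stopping boundary can be written as a Z value or as its nominal p-value, and the two must convert into each other. At the final look they do not. The gap between 0.021 and 0.0238 is too wide for rounding: a p that rounds to 0.021 needs Z between about 2.024 and 2.044.

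The primary result will be reported as a p-value, so a reader may well compare it with the threshold on the p-value scale. If the final Z falls between 1.981 and 2.034, the trial succeeds under one stated criterion and fails under the other, and the fixed sequence carries that outcome to every secondary endpoint. A pivotal trial should not have to choose between two written thresholds after unblinding.

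**Working it through.** **Inputs** (protocol 9.1): one-sided alpha 0.025; O'Brien-Fleming-type spending; one interim at t = 0.60; stated Z boundaries 2.668 and 1.981; stated p boundaries 0.004 and 0.021; "target effects 0.5 vs 0.6114"; 850 participants randomized 1:1; 2% non-evaluable (850 × 0.98 = 833).

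**1. Reproduce the plan's alpha and Z figures.** The spending function is α(t) = 2[1 − Φ(z₁₋α/₂ / √t)].
- α(0.6) = 0.00381, which rounds to the stated 0.004.
- Interim Z = Φ⁻¹(1 − 0.00381) = 2.669 (stated 2.668).
- The final Z is solved so that the total crossing probability is 0.025, with correlation √0.6 between looks. This gives 1.981 (stated 1.981).
- The stated pair 2.668 / 1.981 gives an overall one-sided alpha of 0.0250.

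The spending, both Z boundaries and the total alpha therefore agree with each other.

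**2. Convert to the p-value scale.**
- Interim: 1 − Φ(2.668) = 0.0038, which agrees with 0.004.
- Final: 1 − Φ(1.981) = 0.0238 one-sided, or 0.0476 two-sided. The plan says 0.021.
- In reverse: Φ⁻¹(1 − 0.021) = 2.034. The plan says 1.981.

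**3. Look for a reading that gives 0.021.**
- Two-sided p: 0.0476.
- Classic (non-spending) O'Brien-Fleming at t = 0.6: final Z 1.992, p 0.0232.
- Incremental alpha at the final look: 0.025 − 0.0038 = 0.0212. This is the only match.

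At the first look the nominal p and the alpha spent are the same number, so the interim figure is right under either reading. They separate only at the final look.

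**4. Check the convention against the SAP's 75% design.**
- 1 − Φ(2.34) = 0.0096 (stated 0.01).
- 1 − Φ(2.012) = 0.0221 (stated 0.022).
- Incremental alpha there: 0.025 − 0.0096 = 0.0154, which is not the stated figure.

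The SAP's p-value scale is the nominal p.

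**5. Consequence of applying 0.021 as the final threshold.** Boundaries 2.668 / 2.034 at t = 0.6 give an overall one-sided alpha of 0.0223, a loss of (0.0250 − 0.0223)/0.0250 ≈ 11% of the planned alpha.

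Power (two-look calculation, unpooled variance):

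| Evaluable N | Rates | Final Z 1.981 | Final p 0.021 |
|---|---|---|---|
| 833 | 0.50 vs 0.614 | 91.3% | 90.5% |
| 850 | 0.50 vs 0.614 | 91.8% | 91.0% |
| 833 | 0.50 vs 0.6114 | 90.0% | 89.1% |
| 850 | 0.50 vs 0.6114 | 90.6% | 89.7% |

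The first row reproduces the plan's 91.3%.

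The smallest significant observed difference d, with a 50% placebo rate and n per arm, solves d = z·√{[0.25 + (0.5 + d)(0.5 − d)]/n}, so d = z·√[0.5/(n + z²)].
- n = 425: 6.76 points at Z = 1.981; 6.94 points at Z = 2.034.
- n = 416.5: 6.83 points; 7.01 points.

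**The case against.** The strongest reply concerns weight. The error is conservative, so type I error is not inflated. The disputed band is under 0.2 percentage points of observed difference, and the chance of landing in it is about 0.3% under the null (0.0250 − 0.0223) and 0.8 to 0.9% under the planned effect. The spending function, information fraction, cumulative alpha and Z values fix the boundary uniquely, so a statistician can see that 0.021 is the outlier. No section says outright that the final p-value will be compared with 0.021. All of this is correct, and it limits the practical effect. The discrepancy remains, and SAP section 8.1 does treat its p-scale interim boundary as the critical p-value for stopping, so such figures are read as decision thresholds.

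A second reply is that the SAP already covers the point. Protocol 9.3 gives the SAP precedence, and SAP sections 4.1 and 8.1 say that the final boundary will be adjusted for the alpha actually spent and for a different interim timing. The recomputation principle is indeed there. But the SAP's boundaries belong to a design with 75% information and 680 to 1020 participants, so it supplies no final p threshold for the 60%, 850-participant design. Precedence does not settle which threshold applies.

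Finally, that 0.021 came from the incremental alpha is an inference from the numerical match. The documents do not give its source, and the finding does not depend on it.

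**Conclusion.** The point holds. For the stated design, Z = 1.981 is the correct final boundary and its p-value counterpart is 0.0238 one-sided (0.0476 two-sided). The figure 0.021 is wrong in all three places. It is also incompatible with the total alpha of 0.025 stated alongside it, because together with the interim boundary it yields 0.0223.

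The size is modest: about 11% of the planned alpha, 0.8 to 0.9 points of power, and a shift of just under 0.2 points in the smallest significant difference. It needs correcting because a confirmatory primary test that gates all secondary endpoints should have one threshold. These figures assume an interim at exactly 60% information, Lan-DeMets O'Brien-Fleming-type spending, a 50% placebo rate, and 833 to 850 evaluable participants.

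**What to change.** Replace 0.021 by 0.0238 one-sided (0.0476 two-sided) in the protocol Synopsis and in sections 9.1 and 9.4. Keep four decimals, since 0.024 would lie above the exact level. Add one sentence saying that success is judged against the Z boundary recomputed at the actual information fraction, with the p-value as its nominal equivalent.

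Because the SAP prevails where the two documents differ, it must carry the same boundaries for the 60%, 850-participant design before the correction takes effect.

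Within the protocol the cost is one number in three places and one sentence. Sample size, spending function, Z boundaries and planned power do not change. Make the correction before unblinding, so that it cannot appear to follow from the result.

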9.2 Analysis Sets

For purposes of analysis, the following populations are defined:

Population	Description
Enrolled	All participants randomized into the trial.
Randomly Assigned to Study Intervention	All participants who received a dose or partial dose of study drug

Intent to Treat (ITT)	All participants randomized into the trial with grouping by randomized treatment, regardless of treatment actually received. Participant grouped according to the randomized (intended) treatment.
Per Protocol (PP)	All participants randomized and treated, with no major protocol deviations including: did not meet inclusion/exclusion criteria, did not receive planned dose volume, incorrect study drug vial, infusion more than 15 minutes, consent not obtained.
Safety	All participants randomly assigned to study intervention and who receive any volume of study drug. Participants will be analyzed according to the intervention they actually received.

The primary efficacy estimand analysis will be conducted in the ITT population. The primary efficacy estimand analysis will be repeated on the Per Protocol (PP) population. An ITT analysis will also be conducted for the secondary endpoint estimands, with participant grouped according to the randomized (intended) treatment.

9.3 Statistical Analysis

The statistical analysis plan will be finalized prior to any interim analysis and it will include a more technical and detailed description of the statistical analyses described in this section. In the event that there are any inconsistencies between this protocol and the statistical analysis plan, the statistical analysis will be conducted as per the statistical analysis plan. This section is a summary of the planned statistical analyses of the most important estimand endpoints including primary and key secondary endpoints.

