4 TRIAL DESIGN

4.1 Overall Design

This study is a Phase 3, randomized, multicentre, blinded, placebo-controlled, parallel group, single-dose design with a single interim analysis for safety and efficacy. Because AIS is a medical emergency, the trial is designed to enable the administration of standard-of-care treatments without delay in order to save the life of the person concerned, restore good health or alleviate suffering.

Participants harboring an acute ischemic stroke who are selected for endovascular revascularization without intravenous or intra-arterial thrombolytic therapy will be given a single, 2.6 mg/kg (up to a maximum dose of 270 mg) intravenous dose of nerinetide or placebo. Randomization will be stratified by time from stroke onset to randomization ≤ 4.5 hours (yes/no) and done with stochastic minimization to balance baseline factors within strata. The end of the main trial is defined as the date that the last enrolled participant has completed their Day 90 visit/contact. For the purpose of an analytic follow-up sub-trial component, participants will be contacted by telemedicine or telephone at 1-Year by individuals blinded to the outcome of the main trial.

A total of up to 850 male and female participants aged 18 years and older harboring AIS and who are selected for endovascular revascularization without intravenous or intra-arterial thrombolytic therapy will be enrolled.

All participants in the main trial will be followed for 90 days (or until death if prior to 90 days). At Day 30 and Day 90 it is preferred that participants will return to clinic. If an in-clinic visit is not possible the participant can be contacted by telemedicine (preferred) or by telephone (last option).

Participants will be followed at 1-Year for the analytic sub-trial for further outcome assessment by telemedicine or telephone interview conducted by individuals blinded to the outcome of the main trial. This sub-trial will be conducted to explore the independent functioning and quality of life at 1-Year.

Two database locks and corresponding reports are planned for this trial. The first report will be based on the completion of Day 90 visits for the main trial. The second report will be following the completion of the 1-Year follow up for the analytic sub-trial.

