9 STATISTICS

9.1 Sample Size Determination

The primary estimand will be the adjusted difference in the mRS response (i.e., mRS score of 0-2) proportions between treatment conditions (nerinetide vs. placebo) in the target patient population at Day 90. Participants with mRS score of 0-2 are defined to be responders. Deaths occurring over the Day 90 period will be considered as non-responses.

Primary hypothesis test and 95% confidence interval estimate for the primary estimand will be provided by the analytic method of Ge, 2011^{40} discussed in FDA's most recent draft guidance Adjusting for Covariates in Randomized Clinical Trials for Drugs and Biological Products⁴¹, adjusting for the stratification covariate of time from stroke onset to randomization ≤ 4.5 hours (yes/no) and the randomized minimization factors (age, sex, baseline NIHSS score, baseline ASPECT score, occlusion location, time from qualifying imaging to randomization and pooled site), and an interaction term of treatment by time from stroke onset to randomization. If the interaction term is not significant at the level of 0.05, it will be removed from the model.

Up to 850 male and female participants aged 18 or older harboring AIS and who are selected for endovascular revascularization without intravenous or intra-arterial thrombolytic therapy will be enrolled.

Based on results of ESCAPE-NA1 and assuming a 50% overall responder rate for the placebo group, there will be approximately 91.3% power to detect an 11.4% absolute effect difference between response rate (proportion of responders, with Day 90 mRS in the range 0 to 2) with nerinetide and placebo, at alpha level 0.025 one-sided (0.05 2-sided), using the planned sample size of 850 evaluable subjects, randomized 1:1, per group [EaST v6.5, 2022].

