	The pivotal primary analysis model will be a logistic regression model with fixed effects including the treatment group, the stratification covariate of time from stroke onset to randomization ≤ 4.5 hours (yes/no) and the randomized minimization factors (age, baseline NIHSS score, occlusion location, time from qualifying imaging to randomization, baseline ASPECT score, sex, and pooled site), and an interaction term of treatment by time from stroke onset to randomization. If the interaction term is not significant at the level of 0.05, it will be removed from the model. The odds ratios along with the 95% CI will be reported in addition to the primary Ge et al, 2011 method results. If the interaction term is significant, results will be also reported by randomization stratum separately, using the Ge et al, 2011 method.

Table 9-1: Statistical Analysis Methods

	The secondary analysis in support of the primary analysis will be the two sample proportion Wald test. The risk difference along with the estimated standard error, 95% CI and the Wald test statistics will be reported.
	An additional analysis will be conducted in which the primary analysis is reapplied to the per protocol population with observed cases only.
	Three separate efficacy analysis timepoints are planned for this trial. The first analysis will be at the interim analysis planned at 60% information on the primary endpoint. The second analysis timepoint will be based on the completion of Day 90 visits for the main trial. The third analysis will be following the completion of the 1-Year follow up.

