13.2 Assessment Questionnaires

Below is a sample of the assessment questionnaires and instructions to be used in the trial.

Modified Rankin Scale (mRS)	Clinician Reported Outcome
	English example
National Institute of Health Stroke Score	Clinician Reported Outcome
(NIHSS)	English example.
Barthel Index	Clinician Reported Outcome
	English example.
EQ-5D-5L	Patient Reported Outcome
	USA, English Interviewer Administered example
	See https://euroqol.org/ for device, country, and language specific versions

Statistical Analysis Plan

A Multicentre, Randomized, Double-blinded, Placebo-controlled, Parallel Group, Single-dose Design to Determine the Efficacy and Safety of Nerinetide in Subjects with Acute Ischemic Stroke Undergoing Endovascular Thrombectomy Excluding Thrombolysis

(ESCAPE-NEXT Trial)

Protocol NA-1-009

Product:	Nerinetide
IND:	118,087
Sponsor:	NoNO Inc. [name]
Date	18 November 2021
Version	Final 2.0

SIGNATURES OF APPROVAL

Personal Protected Data

Version History

This Statistical Analysis Plan (SAP) for the trial ESCAPE-NEXT is based on Protocol V5.0, dated 18 November 2021.

Version	Date	Change	Rationale
1.0	03 May 2021	Not Applicable	Original version
2.0	18 Nov 2021	- Updated hierarchical testing order of secondary endpoints: moved the NIHSS responder endpoint to the last.	 The change in testing order of NIHSS endpoint was due to the concern of increased missingness of Day 90 NIHSS scores that may impact statistical power. NIHSS cannot be conducted over the phone. Due to COVID-19 there is an increase in the number of Day 90 visits being conducted by phone.
		 Updated the primary analysis model for all binary efficacy endpoints: a generalized linear regression model with adjustment for baseline covariates and randomization stratification factor will be used Changed one of supportive analyses of the primary efficacy endpoint to an unadjusted logistic regression Added robust estimation of unconditional treatment effect for the primary efficacy endpoint analysis 	- The updates in primary analysis model as well as the addition of unconditional treatment effect were made to be aligned with the FDA draft guidance "Adjusting for Covariates in Randomized Clinical Trials for Drugs and Biological Products" dated in May 2021

TABLE OF CONTENTS

SIGNATURES OF APPROVAL		
Version History		
Table of Contents		
List of Tables		
1 Introduction		

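### The protocol lets an unnamed SAP version govern the analysis, and the only SAP supplied describes a different design, with a different interim boundary at the same 510 participants

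*Combined protocol and SAP*

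**What the plan says.** Protocol 9.3 gives the SAP precedence if there are "any inconsistencies between this protocol and the statistical analysis plan, the statistical analysis will be conducted as per the statistical analysis plan". It names no version. The same section adds, in the future tense: "The statistical analysis plan will be finalized prior to any interim analysis". The SAP supplied is already marked Final 2.0, and its Version History says that it "is based on Protocol V5.0, dated 18 November 2021". The protocol's own calculation cites later software: "planned sample size of 850 evaluable subjects, randomized 1:1, per group [EaST v6.5, 2022" (section 9.1). That 850 is a total, not a number per arm, follows from section 4.1: "A total of up to 850 male and female participants aged 18 years and older".

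The operative texts compare as follows.

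| Item | Protocol | SAP |
|---|---|---|
| Sample size | maximum 850 (4.1, 9.1) | 680 at first, up to 1020 (1.3, 1.4, 8.4) |
| Look at about 510 | 60% information (9.1, 9.4) | 75% information (1.4, 8, 8.1) |
| Z boundaries, interim/final | 2.668 / 1.981 (9.1, 9.4) | 2.34 / 2.012 (1.4, 8.1) |
| Stated p, interim/final | 0.004 / 0.021 | 0.01 / 0.022 |
| Re-estimation | none | unblinded, by conditional power (1.3, 1.4, 8) |
| Pivotal analysis | logistic model, adjusted risk difference by the Ge method (Table 9-1) | log-binomial model, relative risk (6.1.3) |
| Treatment by onset-time interaction | in the pivotal model, dropped if not significant (Table 9-1) | in a supportive model only (6.1.3) |

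In the protocol's words, "the stopping boundaries on the Z scale are 2.668 (interim) and 1.981 (final") and "on the p-value scale 0.004 (interim) and 0.021 (final"). Table 9-1 repeats the timing: "The first analysis will be at the interim analysis planned at 60% information on the primary endpoint".

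**The concern.** Both documents plan an unblinded efficacy look at the same number of participants, but they call it a different fraction of a different total and attach different thresholds. A reader who applies the precedence clause to the SAP in hand arrives at the boundary of a 680-participant adaptive design, while the protocol enrols up to 850 and describes no re-estimation. The clause speaks of the statistical analysis, so it is unclear whether it reaches enrolment and maximum sample size.

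The threshold at which the independent data monitoring committee would be told that the efficacy boundary is crossed is therefore not uniquely fixed in advance. That cannot be repaired credibly once unblinded data have been seen. The clause would also change the pivotal model and the reported effect measure, although SAP 4.2 and 6.1.1 still define the primary estimand as a difference in proportions.

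**Working it through.** **Inputs.** One-sided alpha 0.025, O'Brien-Fleming spending, 510 participants at the look (both documents); maximum 850 (protocol 4.1, 9.1) or initial 680 (SAP 1.4); response rates 0.50 vs 0.6114 (protocol 9.1). The protocol also describes the effect as 11.4 points; 0.6114 − 0.50 is 11.14 points, and that is used below.

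**1. Each document's own boundaries.** Lan-DeMets spending: α(t) = 2[1 − Φ(z/√t)], with z = Φ⁻¹(1 − 0.0125) = 2.2414. The final boundary solves P(Z₁ < c₁, Z₂ < c₂) = 0.975, with correlation √t.

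- Protocol, t = 510/850 = 0.60: 2.2414/√0.60 = 2.894, so α₁ = 0.0038; Z 2.669 / 1.981.
- SAP, t = 510/680 = 0.75: 2.2414/√0.75 = 2.588, so α₁ = 0.0096; Z 2.340 / 2.012, final p 0.0221.

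Both printed sets of Z boundaries reproduce, and each gives an overall one-sided alpha of 0.0250. They are two valid but different designs.

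**2. What the difference means at the interim.** Unadjusted Wald statistic, 255 per arm:

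- SE = √[(0.50×0.50 + 0.6114×0.3886)/255] = √[(0.2500 + 0.2376)/255] = 0.0437; expected Z = 0.1114/0.0437 = 2.548.
- P(cross 2.34) = 1 − Φ(2.34 − 2.548) = 0.582.
- P(cross 2.668) = 1 − Φ(2.668 − 2.548) = 0.452.
- P(Z between the two) = 0.582 − 0.452 = 0.130; under the null, 0.0058.
- With 50% placebo response, the observed difference needed to cross is about 10.3 points (SAP) or 11.7 points (protocol).

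**3. Mixing the printed boundaries at t = 0.60.** With 2.34/2.012 the overall one-sided alpha is 0.0266; with 2.34/1.981 it is 0.0281. After 2.34 at the interim, a final Z of 2.048 would be needed to hold 0.025.

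**4. Effect measure.** At the two observed differences in step 2, the unadjusted Z is about 2.34 and 2.67 for the risk difference, and 2.31 and 2.63 for the log relative risk. The shift is 0.03 to 0.04. SAP 6.1.3 Steps 3 and 5 give standardized response rates from which a difference could be formed, but Step 6 and the bootstrap interval are for the relative risk.

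**5. Protocol final p-value.** 1 − Φ(1.981) = 0.0238. The printed 0.021 corresponds to Z 2.034; it equals 0.025 − 0.004, the increment in alpha spent. Testing at 0.021 after 2.668 at the interim gives an overall alpha of about 0.0223. The same figure stands in the Synopsis and in protocol 9.1 and 9.4.

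**The case against.** The strongest reply is that a later, aligned SAP may be intended. Protocol 9.3 expects the SAP to be finalized before any interim analysis, and the supplied SAP names an earlier protocol. That the supplied SAP predates the protocol is itself an inference from the 2021 date and the 2022 software citation. This limits the point to the documents in hand. It does not remove it, because the SAP supplied is labelled final, the clause names no version, and no other SAP is supplied.

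Second, a reader might infer from step 3 that the plan inflates the type I error. The documents do not support that. Both print their boundaries on a stated information fraction. SAP 4.1 adjusts the final boundary to the alpha actually spent at the interim, and SAP 8.1 recalculates the boundaries if the look is not at 75% and supplies the committee with boundaries for the correct information time. The figures 0.0266 and 0.0281 arise only if printed values are carried over against those instructions. The recalculation clauses do not settle the conflict, however. With the SAP's denominator of 680, 510 participants is exactly 75%, so nothing prompts a move to the protocol's boundaries.

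Third, read literally, the clause does settle the pivotal model and the interaction rule, in the SAP's favour. That is fair. What remains is that the result would be reported as a relative risk against an estimand defined as a difference. Equal proportions is the same null on either scale, so this matters for the estimate and its interval more than for the test.

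Fourth, crossing does not oblige the committee to recommend stopping (protocol 9.4, SAP 8.1). That stands; what differs is whether a crossing is reported.

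**Conclusion.** The point holds. The interim threshold, the maximum sample size and the presence of re-estimation are not uniquely specified across the two documents, and the precedence clause makes this worse by pointing to an unnamed SAP version. The size is about 58% against 45% for crossing at the interim under the design effect, with about a 13% chance that the two documents give different answers on the same data. These probabilities assume 255 per arm, 0.50 vs 0.6114 and an unadjusted Wald test; the planned tests adjust for covariates, so the exact values will differ.

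The effect measure and the interaction rule are secondary. The final p-value of 0.021 is a separate error within the protocol, and using it would make the final test conservative.

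It does not follow that the error rate is already lost, that the trial is bound to enrol up to 1020, or that the interim will be run under conflicting rules. The confidence here attaches to the conflict in the text and to the arithmetic.

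**What to change.** Before the interim analysis:

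1. Reissue the SAP so that it names and matches the current protocol version: N = 850, no re-estimation, and one look at 60% information with Lan-DeMets O'Brien-Fleming boundaries 2.668/1.981, recomputed at the actual information fraction.
2. In SAP 6.1.3, replace the log-binomial model, including Step 1 of the unconditional estimate, by the protocol's logistic model with the Ge method. Report the risk difference with that method's confidence interval in place of the Step 6 relative risk. Changing Step 6 alone would leave the model conflict in place.
3. State one identical rule for the treatment by onset-time interaction in both documents.
4. Correct the protocol's final one-sided p to 0.0238 wherever 0.021 appears.
5. Limit the precedence clause in protocol 9.3 to a SAP version that names the current protocol version.

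This takes the protocol as the current design. The cost is a SAP revision and a few sentences in the protocol, with no extra participants or data.
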